10.1.2. Serious Adverse Event

An SAE is any AE occurring at any dose that results in any of the following outcomes:

- death
- a life-threatening event
 - This includes any AE that in the view of either the investigator or sponsor places the subject at immediate risk of death. It does not include an AE that, had it occurred in a more serious form, might have caused death.
- requires inpatient hospitalization or prolongs existing hospitalization
 - Hospitalization signifies the subject has been admitted, regardless of duration, for observation and/or treatment that would not have been appropriate in a physician's office or outpatient setting.
 - Hospitalizations for elective or pre-planned treatment of a pre-existing condition do not have to be reported as SAEs if the following criteria are met:
 - the condition is documented in the subject's medical history and has not worsened since the informed consent form was first signed; and
 - the condition and planned procedure are documented in the subject's source records at baseline.
 - Emergency room/department or outpatient treatments that do not result in admission do not have to be reported as an SAE, unless another SAE criterion is met. Events assessed and treated in these circumstances should be captured as AEs in the eCRF and documented in the subject's source records.
 - Hospitalizations solely based on subject logistics (eg, subject is admitted due to limited hospital accessibility for what would otherwise be an out-subject procedure) do not have to be reported as SAEs provided that the hospitalizations are clearly defined as such in the subject's source record.
- persistent or significant incapacity or substantial disruption of the ability to conduct normal life functions
- congenital anomaly/birth defect

An important medical event that does not result in one of the above serious outcomes may be considered an SAE when, based upon appropriate medical judgment, it may jeopardize the subject and may require medical or surgical intervention to prevent one of the listed serious outcomes. Examples of such medical events include allergic bronchospasm requiring intensive treatment in an emergency room or at home, blood dyscrasias, or convulsions that do not result in inpatient hospitalization, or development of drug dependency or drug abuse.

If the following 4 elements are known, the event must be reported as described in Section 10.4.2:

- identifiable subject
- event term
- study drug
- identifiable reporter

Additionally, the investigator's assessment of an event's relationship to study drug (see Section 10.2) is essential for Amicus to appropriately process the report and must be included.

Subjects and parents or legally-authorized representatives must be informed and understand that they should report events meeting the definition for SAE to study site personnel as soon as possible (and not wait until their next study visit).

If a non-serious event becomes serious, the change in status must be appropriately entered in the eCRF and the subject's source record, and reported to Amicus as described in Section 10.4.2.

If the investigator becomes aware of an SAE that occurs more than 30 days after the last dose of study drug, and considers the event possibly, probably, or definitely related to study drug, the investigator should contact the medical monitor (see Table 1) or the Clinical Operations Lead to determine how the SAE should be documented and reported.

10.2. Relationship to Study Drug

The investigator or a medically qualified sub-investigator will review each event and assess its relationship to study drug based on available information and according to the following guidelines:

- Definite: a reaction that follows a distinct temporal relationship from administration of study drug; that follows a known reaction to the agent or chemical group of the study drug; and that cannot be explained by the subject's clinical state or other factors
- Probable: a reaction that follows a reasonable temporal sequence from administration of study drug; that follows a known or expected response pattern to the suspected study drug; and that could not be reasonably explained by the known characteristics of the subject's clinical state
- Possible: a reaction that follows a reasonable temporal sequence from administration of study drug; that follows a known or expected response pattern to the suspected study drug; but that could readily have been produced by a number of other factors
- Unlikely: a reaction that does not follow a reasonable temporal sequence from administration of study drug; however, causality from the study drug cannot be ruled out
- Unrelated: a reaction for which sufficient data exist to indicate that the etiology is unrelated to study drug

For the purpose of expedited SAE regulatory reporting obligations (ie, to regulatory authorities and Institutional Review Boards [IRBs]/Independent Ethics Committees [IECs]), events assessed by the investigator as definitely, probably, or possibly related to study drug will be considered "related" to study drug (ie, associated with the use of study drug). Events assessed as unlikely or unrelated will be considered "not related" to study drug (ie, not associated with the use of study drug).

10.3. Severity Assessment

The investigator or a qualified sub-investigator will review each event and use the following definitions for rating intensity:

- Mild: awareness of sign, symptom or event, but the AE is easily tolerated and does not interfere with daily activity
- Moderate: discomfort enough to cause interference with usual activity and may warrant intervention, but the subject is still able to function
- Severe: incapacitating with inability to do usual activities or significantly affects clinical status, and requires medical intervention

It is important to distinguish the difference between events that meet the definition of serious and events that are deemed as severe in intensity. Adverse events assessed as severe in intensity are not SAEs unless at least 1 of the definitions in Section 10.1.2 is met. Adverse events of any intensity must be reported as SAEs if at least 1 definition in Section 10.1.2 is met.

10.4. Reporting Events

10.4.1. Reporting Adverse Events

Information regarding AEs is to be obtained by questioning or examining the subject and/or parents or legally-authorized representatives.

As noted in Section 10.1.1, AEs will be recorded in the eCRF and subject source record beginning from the time written consent (assent) is provided through the follow-up visit (at least 30 days after the last dose of study drug). Required information will be detailed in the eCRF Completion Guidelines.

10.4.2. Reporting Serious Adverse Events

Serious adverse events must be documented and reported to Amicus immediately, but no later than within 24 hours of any knowledge by study site personnel of events. Serious adverse event reports must be faxed to the designated safety fax number (Table 1) to ensure appropriate dissemination and processing of the information. An alternate email address is provided as a backup, if the fax transmission is unsuccessful.

Serious adverse event forms, which will be provided by Amicus, should be as complete as soon as possible, and should include all information known at the time. All relevant supporting documentation (eg, admission and progress notes, results of diagnostic evaluations/procedures/ examinations, etc) available at the time of reporting, should be included in the fax (or email, if necessary) along with the SAE report form. All supporting documents must be thoroughly reviewed and de-identified in accordance with local data privacy regulations prior to sending to Amicus. The subject's study number must be included on each page included in the faxed report or in the subject line of the email. Reporting timelines (as described above) must not be delayed while obtaining or preparing supporting information.

If more than 1 SAE is identified in 1 subject simultaneously, separate SAE reports should be generated for each event.

Information not available at the time of the initial report (eg, event end date and outcome, supporting documents [eg, discharge summary, etc]) must be reported to Amicus within **24 hours of any knowledge/receipt by study site personnel of the information**. Information must be faxed (or emailed, if necessary) to the designated safety fax number (or email address) (Table 1) to ensure appropriate dissemination and processing. All supporting documents must be thoroughly reviewed and de-identified in accordance with local data privacy regulations prior to sending to Amicus. The subject's study number must be indicated on each page included in the fax or in the subject line of the email.

Medical history, concomitant medication, and AE information obtained through SAE reporting must also be consistently recorded in the eCRF.

10.4.3. Additional Reporting Requirements for Suspected Unexpected Serious Adverse Reaction

The sponsor is responsible for processing suspected unexpected serious adverse reactions (SUSARs). SUSARs are also referred to as alert reports, expedited safety reports, and investigational new drug application (IND) safety reports.

A SUSAR is defined as any SAE that is determined to be associated with the use of study drug and is unexpected (not currently listed in the safety reference information or is not listed at the specificity or severity that been observed). The sponsor will notify all investigators currently conducting migalastat clinical studies of all SUSARs in accordance with applicable regulations. SUSARs will be reported to the relevant regulatory authorities and IRBs/IECs according to the rules in effect in each country where study sites are located:

- If the SUSAR is fatal or life-threatening, regulatory authorities and ethics committees will be notified within 7 calendar days after Amicus learns of the event.
- If the SUSAR is not fatal or life-threatening, regulatory authorities and ethics committees will be notified within 15 calendar days after Amicus learns of the event.

These notifications will need to be filed in each site's Study File Notebook and submitted to each site's IRB/IEC in accordance with policy.

Safety updates will be provided periodically to the regulatory authorities and IRBs/IECs responsible for the study according to the rules in effect in each country where study sites are located. These updates will include information on SUSARs and other relevant safety findings.

10.5. Other Reporting Situations

10.5.1. Pregnancy

Pregnancy information for female subjects and female partners of male subjects participating in the study is collected by Amicus. Pregnancy, in and of itself, is not regarded as an AE (unless there is a suspicion that study drug may have interfered with the effectiveness of a contraceptive medication).

If a female subject becomes pregnant during the course of the study, or if the female partner of a male subject becomes pregnant during the subject's participation in the study, Amicus must be informed within 5 working days of any knowledge of the pregnancy by study site personnel. If an SAE occurs in conjunction with the pregnancy, the SAE must be reported as described in Section 10.4.2. The sponsor will provide pregnancy report forms (initial and follow-up) and instructions to study site personnel regarding collection of pregnancy and outcome information (subject to receipt of data privacy release approvals where required under local privacy laws). Pregnancy report forms must be faxed (or emailed, if necessary) to the designated safety fax number (or email) (Table 1) to ensure appropriate dissemination and processing of the information.

10.5.2. Medication Errors, Including Overdose and Under Dose

Medication error refers to any unintended error in the dispensing or administration of a study drug.

If a subject experiences an overdose (defined as $\geq 20\%$ higher than the assigned dose of study drug for that period in the protocol) or an under dose (defined as $\geq 20\%$ lower than the assigned dose of study drug for that period in the protocol) during the course of the study (whether symptomatic or not), the Amicus' medical monitor must be notified within 5 working days of the investigator or study staff first becoming aware of the overdose.

Medication errors, including overdose and under dose, should be captured in subjects' source records and recorded in the eCRFs. Any AE or SAE that occurs as a result of a medication error should be reported according to AE/SAE reporting requirements (see Section 10.4).

10.5.3. Reporting of Possible Study Drug Product Quality Defects

Any defect or possible defect associated with study drug must be reported to Amicus ([contact]) within 1 working day of any study site personnel knowledge of the possible defect. The study drug and packaging components in question, if available, must be segregated and stored in a secure area at the site under the specified storage conditions (see Section 12.3.1) until it is determined whether or not the study drug and/or packaging is required for investigation of the possible defect. If the possible defect is associated with an SAE, the SAE must be reported as described in Section 10.4.2. The SAE report must include the possible study drug defect complaint.

11. DATA ANALYSIS AND STATISTICAL CONSIDERATIONS

Details of the data handling rules and statistical calculations will be provided in the statistical analysis plan (SAP).

11.1. Endpoints

11.1.1. Safety Endpoints

Safety endpoints are as follows:

- incidence of TEAEs, SAEs, and AEs leading to discontinuation of study drug
- change from baseline in clinical laboratory test results over time
- change from baseline in vital signs over time
- change from baseline in physical examination findings over time
- change from baseline in body weight and height over time
- change from baseline in ECG results over time
- change from baseline in echocardiogram parameters over time
- change from baseline in Tanner Stage

11.1.2. Pharmacodynamic Endpoints

The PD endpoint is the change from baseline in plasma levels of lyso-Gb₃.

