6.2. Secondary Objectives

The secondary objectives of this study are as follows:

- to characterize the PD of migalastat in pediatric subjects diagnosed with Fabry disease and who have *GLA* variants amenable to treatment with migalastat
- to assess the efficacy of migalastat in pediatric subjects diagnosed with Fabry disease and who have *GLA* variants amenable to treatment with migalastat

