Abbreviations: BP = blood pressure; ECG = electrocardiogram; eGFR = estimated glomerular filtration rate; EOT = end of treatment; ET = early termination; FPHPQ = Fabry-Specific Pediatric Health and Pain Questionnaire; HR = heart rate; LMP = last menstrual period; LVMi = left ventricular mass index; lyso-Gb₃ = globotriaosylsphingosine; PD = pharmacodynamic; PedsQL = Pediatric Quality of Life Inventory; RR = respiration rate; TC = telephone call; Temp = body temperature

Note: Following Month 24, visits will continue every 6 months with interim telephone contacts at 3-month intervals. The assessment schedule will repeat starting from Month 3.

Note: For the purposes of this study, a month is considered to be 30 days.

^a End of study assessments from Study AT1001-020 will be used as baseline assessments for Study AT1001-036.

^b A dosing diary will be completed throughout the treatment period.

^c Female subjects only; urine pregnancy tests will be conducted at each site visit. For menstruating females, date of LMP will be elicited during telephone contacts.

^d Return of study drug only.

Assessments	Baseline ^a	Month 6	Month 12	Total
Chemistry	4	4	4	12
Hematology	2	2	2	6
Plasma lyso-Gb ₃ and PD biomarkers	4	4	4	12
			Total:	30 mL

Table 3: Total Blood Volume to be Collected (as Scheduled) per Subject per Year

Abbreviations: lyso-Gb₃ = globotriaosylsphingosine; PD = pharmacodynamic

Note: Total collection volume does not take into account additional blood samples drawn during potential unscheduled visits.

^a End of study laboratory assessments for Study AT1001-020 will be used as Visit 1 assessments for Study AT1001-036. The blood volume from baseline assessments should not be counted for subsequent years.

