11.4. Statistical Methods

For the purpose of statistical analyses, baseline is generally defined as the last non missing measurement obtained on or before the administration of the first dose of study drug. For this study, the baseline value for efficacy endpoints will be obtained from the baseline visit of Study AT1001-020.

Only summary statistics will be provided for data collected from this study. No missing data imputation method is planned to handle missing data. Data will be summarized as observed.

Data will be summarized using descriptive statistics. Continuous variables will be summarized by number of subjects, mean, standard deviation, median, minimum, and maximum values. Discrete variables will be summarized by counts and percentages.

In general, data will be summarized by age group at baseline, by sex, and combined across all subjects.

A month will be defined as 30 days.

No missing data imputation method is planned to handle missing data. Data will be summarized as observed. All data will be listed.

Full details will be presented in the SAP.

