5.5. Baseline Definition

For all safety, PD, and efficacy data, the baseline value is defined as the last non-missing measurement obtained on or before the administration of the first dose of study drug in Study AT1001-036 (Day 1).

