8.1. Primary PD Endpoint and Analysis

The PD endpoint is change in plasma levels of lyso-Gb3. Descriptive summaries will be provided for the observed and change from baseline values to Month 6, and Month 12 by sex (male and female), ERT status (ERT naïve, ERT experienced), and overall based on the enrolled population.

A by-subject listing will also be provided.

9. Safety

The analysis population used for safety analyses will be the enrolled population. Safety will be assessed on the basis of extent of exposure, incidence of TEAEs, SAEs and AEs leading to discontinuation, clinical laboratory data, vital signs including body weight and height, ECG parameters, physical examinations, and Tanner stage.

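### The planned lyso-Gb3 change score starts from a value normally taken on migalastat, so it describes maintenance during AT1001-036 and omits any response already reached in AT1001-020

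*Protocol*

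**What the plan says.** One secondary objective is "to characterize the PD of migalastat in pediatric subjects diagnosed with Fabry disease" (Protocol 6.2). It has a single endpoint, worded in Protocol 11.1.2 as follows: "The PD endpoint is the change from baseline in plasma levels of" lyso-Gb3. SAP 2.2.2 agrees, and the protocol synopsis calls plasma lyso-Gb3 the primary PD biomarker.

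The baseline is set in three places:

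- **SAP 5.5** applies one rule to safety, PD and efficacy alike. The baseline it names is "the last non-missing measurement obtained on or before the administration of the first dose of study drug in Study AT1001-036 (Day 1").
- **Protocol 11.4** gives a general rule, under which "baseline is generally defined as the last non missing measurement obtained on or before the administration of the first dose of study drug". It does not say which study's first dose is meant. It then makes one exception: "For this study, the baseline value for efficacy endpoints will be obtained from the baseline visit of Study AT1001-020". Lyso-Gb3 is not on the efficacy list in Protocol 11.1.3.
- **Protocol Table 2, footnote a**, fills the Baseline column, which includes lyso-Gb3: "End of study assessments from Study AT1001-020 will be used as baseline assessments for Study AT1001-036".

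Subjects stay on their AT1001-020 dose (Protocol 7.1) and treatment is meant to be uninterrupted. Only a gap of more than 30 days requires Visit 1 to be repeated (Protocol 9.1.2).

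For the analysis, SAP 8.1 plans descriptive summaries of observed lyso-Gb3 as well as change from baseline, to Months 6 and 12, by sex, ERT status and overall, plus a by-subject listing. Protocol 11.4.5 also summarizes the levels.

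**The concern.** A change score removes whatever is already in its baseline. If a subject's lyso-Gb3 fell during AT1001-020 and that lower value becomes the baseline, the fall is subtracted out. What remains is movement after AT1001-036 Day 1. The number is useful, but it answers whether the response held, not how far lyso-Gb3 has moved since migalastat was started.

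Two things are at stake. First, this is the only PD endpoint for a stated secondary objective, and a mean change near zero could be misread in either direction: as no effect, or as a sustained one. Second, the protocol reports eGFR, urine protein and albumin, LVMi and both questionnaires from the start of AT1001-020. PD reported from the end of that study could not be set beside them over the same period.

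This is separate from another discrepancy: SAP 5.5 also applies the AT1001-036 baseline to efficacy, against Protocol 11.4. Correcting that alone would leave lyso-Gb3 where it is.

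**Working it through.** The plan states no sample size, power or expected effect, so there is no figure to reproduce. The check applies the SAP's own change rule to assumed profiles.

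**Inputs from the documents.** Change = visit value minus baseline value (SAP 5.6.1.4). PD baseline = last value up to the first AT1001-036 dose (SAP 5.5).

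**Assumptions, not in the documents.** Lyso-Gb3 index of 100 at the AT1001-020 baseline, taken to precede any migalastat. Fractional reduction *r* by the end of AT1001-020 of 0, 0.2, 0.4 or 0.6. Drift *d* during AT1001-036 of -10%, 0 or +10%. No treatment gap over 30 days.

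**Formulas.** Day 1 level D = 100(1 - r). Later level V = D(1 + d). Planned change = V - D. Change since starting migalastat = V - 100, which on this index is also the percent change.

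| r | D | V at d = -10%, 0, +10% | V - D | V - 100 |
|---|---|---|---|---|
| 0% | 100 | 90, 100, 110 | -10, 0, +10 | -10, 0, +10 |
| 20% | 80 | 72, 80, 88 | -8, 0, +8 | -28, -20, -12 |
| 40% | 60 | 54, 60, 66 | -6, 0, +6 | -46, -40, -34 |
| 60% | 40 | 36, 40, 44 | -4, 0, +4 | -64, -60, -56 |

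With no drift the planned change is 0 in every row, while the change from the AT1001-020 baseline runs from 0 to -60. Expressing the planned change as a percentage does not help: it equals *d* whatever *r* was (for example -10/100 = -4/40 = -10%).

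**Do the observed levels close the gap?** Take three assumed subjects, with values at AT1001-020 baseline, AT1001-036 Day 1 and Month 12.

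- A: 20, 8, 8. Planned change 8 - 8 = 0; since starting migalastat 8 - 20 = -12, or -12/20 = -60%.
- B: 20, 20, 20. Planned change 0; since starting 0.
- C: 8, 8, 8. Planned change 0; since starting 0.

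Observed levels separate A from B (8 against 20). They do not separate A from C, which look identical in every planned lyso-Gb3 output although one fell by 60% and the other did not change. Differing starting levels are plausible: Protocol 5.1 describes a spectrum of severity and variable expression in females, and SAP 8.1 covers both ERT-naïve and ERT-experienced subjects.

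**Treatment gap over 30 days.** Visit 1 is repeated, so the baseline may be off drug. With r = 60%, suppose 0%, 50% or 100% of the reduction is lost in the gap and then regained. The baseline is 40, 70 or 100, the later level is 40, and the planned change is 0, -30 or -60. For such a subject the score need not be zero and means something different.

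**The case against.** The strongest reply is that change from AT1001-036 Day 1 is a legitimate choice for an extension, where durability is the new information. The objective is only to characterize PD, without hypothesis or test, and observed levels are summarized and listed. Much of this stands. A reader might infer that the PD objective cannot be answered; the documents do not support that, because the planned outputs do describe levels and durability. What they lack is one derived quantity, the change since starting migalastat.

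Three further points limit the claim:

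- A reader might infer that both documents state this baseline outright. Only the SAP does. Footnote a does not settle the protocol's position: it also covers eGFR, echocardiography and the questionnaires, whose analysis baseline Protocol 11.4 nevertheless puts at the AT1001-020 baseline visit. If the general rule means the first AT1001-020 dose, SAP 5.5 departs from the protocol for PD, and SAP section 12 does not say so. Either reading needs clarification.
- A reader might take scores near zero as a fact. They depend on stable levels and no gap over 30 days. If untreated disease progression raised a non-responder's level by 10% while a responder stayed flat, the planned change would separate them (+10 against 0).
- A reader might infer that a planned ERT-naïve versus ERT-experienced comparison is undermined. SAP 8.1 plans subgroup summaries, not a formal contrast, and SAP 5.4.3 has no p-values.

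What the reply does not meet is the A-against-C case: without the pre-treatment level, observed AT1001-036 values cannot show response since starting migalastat.

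**Conclusion.** The point holds as a moderate gap that should be closed. Explicitly in the SAP and by default in the protocol, lyso-Gb3 change is measured from a value normally taken on migalastat. It therefore describes maintenance or drift in AT1001-036 and leaves out any reduction already achieved. Under stable levels and no gap over 30 days, the omission equals the whole earlier response: 0 reported in place of -20, -40 or -60 on the assumed index.

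The size is illustrative. The documents give no lyso-Gb3 values, no time course and no AT1001-020 duration. The conclusion also assumes that the AT1001-020 baseline precedes migalastat. That the score is anchored on treatment, and that neither document plans to use the AT1001-020 baseline value for PD, comes from the documents and does not depend on the assumed numbers.

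**What to change.** 1. In SAP 8.1, and correspondingly in Protocol 11.4, add change and percent change in lyso-Gb3 from the pre-treatment AT1001-020 baseline at each AT1001-036 visit with a lyso-Gb3 sample, by sex, ERT status and overall. Show the AT1001-020 baseline value in the listing. This assumes the value was collected in AT1001-020, which the documents do not confirm.
2. Keep change from AT1001-036 Day 1 and label it maintenance of response. Identify subjects whose Visit 1 was repeated after a gap over 30 days.
3. State in Protocol 11.4 which study's first dose defines the PD baseline, align SAP 5.5 with it, and record any departure in SAP section 12.

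The cost is wording and a small data merge, with no new samples. Data linkage to AT1001-020 is already needed for demographics (Protocol 11.4.2) and ERT status (SAP 6.2). The protocol wording would go through the amendment or clarification route in Protocol 14.1.8.

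The added measure has limits that should be stated with it. In an uncontrolled study it remains descriptive and does not isolate the drug effect, and in ERT-experienced subjects the AT1001-020 baseline may reflect earlier ERT.
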